---

# **The Efficacy of Circuits-based Neuromodulation on Long-term Delayed Recall in Amnestic Mild Cognitive Impairment: A Pilot, Randomized, Controlled Clinical Trial Study Protocol**

## **Background**

With the global population entering an aging phase, Alzheimer's Disease (AD), a neurodegenerative disease closely associated with age, has gained increasing attention from scholars. Due to the unsatisfactory efficacy of current AD treatments, early detection and diagnosis have become a focus of medical researchers, in addition to treatment-related studies. Against this background, amnestic Mild Cognitive Impairment (aMCI), which is considered to be an intermediate stage between normal cognitive aging and early AD, has received growing attention and research.

Transcranial magnetic stimulation (TMS) is a non-invasive and minimally side-effect neural modulation technique that plays a significant role in cognitive neuroscience and clinical neural functional regulation. TMS utilizes the induction of electric fields generated by pulsed currents to modulate neuronal excitability within brain tissue, allowing for targeted stimulation of specific cortical brain regions and improving cognitive functions in humans and animals. In recent years, using TMS for neural modulation to improve cognitive functions has become a hotspot of interest among researchers in neurorehabilitation. However, current research and clinical applications mostly focus on single-target treatments, which have shown limited effectiveness. Therefore, there is an urgent need to explore novel TMS-based rehabilitation strategies.

With the emergence of the concept of the "human connectome", people have gradually realized that different brain regions leading to similar symptoms may be part of a common network with interconnections. Fox et al. [1], in their publication in *The New England Journal of Medicine*, argued that lesion-based localization

---

sometimes has limitations because damage to different brain locations may result in similar symptoms. For example, most language impairment is located outside the left frontal cortex, most memory impairment is located outside the hippocampus, and impairment of social behavior is typically located outside the frontal cortex. Even among patients with similar symptoms, lesion overlap and the overlapping locations may not align with traditional understanding of the corresponding brain functions. For instance, brainstem lesions causing visual hallucinations overlap in the midbrain and thalamus, but these locations do not have a clear role in vision or visual imagery. Therefore, the relationship between symptoms and lesion location is not direct. Another limitation of lesion-based localization is that many complex symptoms occur in patients without obvious brain damage. Common neurological and psychiatric disorders, such as delirium, amnesia, autism, and schizophrenia, often occur in patients without apparent brain damage. Complex symptoms may not be limited to a single brain region but can map to larger distributed brain networks. Damage to any region within these networks may disrupt behavior and lead to similar symptoms. For example, solving complex problems requires the coordinated function of frontal and parietal regions, and impairment in any of these areas would diminish performance. Similarly, damage to interregional connections can result in complex "disconnection" syndromes while the cortical areas necessary for the behavior remain intact. This article proposes a new approach based on identifying treatment targets within the damaged brain network.

Hebbian plasticity is an excitatory synaptic plasticity learning rule that activates when presynaptic and postsynaptic neurons are active simultaneously, resulting in the strengthening of functional connections between neurons (i.e., "fire together, wire together"). If this mechanism is repeatedly activated, the plasticity can shift from a functional level to a structural level, leading to the induction of new synaptic connections and long-term maintenance of functionality. Therefore, Hebbian plasticity is a crucial mechanism for brain circuit reconstruction and can establish new compensatory neural circuits in the brain after circuit damage by activating appropriate presynaptic and postsynaptic neurons, thereby restoring impaired

---

functionality [2].

Cortico-cortical paired associative stimulation (ccPAS), based on Hebbian theory, enhances or weakens synaptic transmission efficiency based on the timing interval (inter-stimulus interval, ISI) between two different sources of stimulation that converge on the postsynaptic neurons of cortical pyramidal cells. If a weak input signal is reinforced before activating the postsynaptic neurons, synaptic transmission efficiency is enhanced, resulting in long-term potentiation (LTP). Conversely, if the input signal follows the activation of postsynaptic neurons, synaptic transmission efficiency is weakened, leading to long-term depression (LTD). By adjusting the ISI, ccPAS can produce different effects on cortical excitability [3].

In summary, we believe that the use of ccPAS to modulate neural circuits based on the Hebbian model can improve cognitive function. In this study, we propose to conduct a randomized controlled trial with aMCI patients as the research subjects. By using behavioral measures (neuropsychological tests, activities of daily living, depression and anxiety scales) and multimodal magnetic resonance imaging, we aim to objectively evaluate the effects of TMS on memory function and central reorganization patterns, thereby developing an optimized cognitive rehabilitation program and suitable techniques. This research will establish an optimized cognitive rehabilitation program and suitable techniques, providing not only objective theoretical and practical foundations for clinical treatment but also contributing to the popularization and promotion of aMCI rehabilitation programs and appropriate techniques.

## **Objective**

The aim of this study is to investigate the effects of cortico-cortical paired associative stimulation (ccPAS) on cognitive function and central reorganization patterns in individuals with amnesic mild cognitive impairment (aMCI) by comparing it to a sham stimulation group and assessing pre- and post-treatment outcomes.

## **Method**

a parallel-group, randomized, controlled clinical trial.

## **Object**

### **Source of cases**

Participants were recruited from the rehabilitation center at Yueyang Hospital of Integrated Traditional Chinese and Western Medicine, Shanghai University of Traditional Chinese Medicine.

### **Sample size calculation**

Sample size calculation was calculated based on long delay recall score as the main observation index. As this study adopts a new treatment method, sample size was acquired from our preliminary study. As a result, the mean (5.1) and standard deviation (2.23) after treatment, as well as the mean (2.6) after false stimulation, a minimum total sample size of 33 treatment-completers was required to achieve 90% power at  $\alpha=0.05$ . To account for attrition and ensure adequate power at 2 weeks after treatment, 42 participants need to be included, with 21 subjects in each group.

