## Outcome

1. The primary outcome is change from baseline in long-term delayed recall performance (Delta AVLT\_N5) following the ccPAS intervention compared with the sham stimulation group.
2. Secondary outcome measures is also recorded as the primary outcome, included MMSE, other AVLT items, STT, SDMT, BNT, CFT. In exploratory analyses, we will assess the relationship of changes in cognitive performance and FC.

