## Statistical analysis

SPSS 21.0 (SPSS Inc., Chicago, Illinois) software will be used for statistical analysis in clinical data. The statistical description of measurement data is expressed by mean  $\pm$  standard deviation. The comparison of the two groups of mean: when it conforms to the normal distribution and homogeneity test of variance, the independent sample t test is used.

The stimulation targets related to long-term delayed recall will be identified by analyzing the relationship between FC of “cortex-hippocampus” circuit and AVLT long delayed memory performance in aMCI patients. Using the left hippocampus as the seed point, ROI based FC analysis to the cortical brain area of the “cortex-hippocampus” network will be calculated. A generalized linear model will be constructed with AVLT\_N5 score as dependent variable and every FC value of left “hippocampus-cortex” network as independent variable.

The repeated measurement ANOVA will be performed in comparison between the treatment group and sham stimulation group before and after treatment, the test of intra subject effect will be corrected by Greenhouse-Geisser, and the post test will be performed by LSD method. Effect sizes (Cohen’s d) will be interpreted as small = 0.2, medium = 0.5, large = 0.8. Non parametric test shall be adopted when it does not

---

conform to normal distribution or homogeneity of variance. The counting data will be expressed by frequency/rate, and the comparison between the two groups will be made by chi square test or Fisher exact probability method. The  $p < 0.05$  (two-sided) indicates significant statistical difference. GraphPad Prism 6 will be used for drawing.

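### The 90% power claimed for 33 completers is calculated on after-treatment scores, not on the change from baseline that is the primary outcome, and on its own inputs the two-sided t test needs 36

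*Protocol*

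**What the plan says.** The protocol's section Sample size calculation names the variable used: "Sample size calculation was calculated based on long delay recall score as the main observation index". The inputs come from the sponsor's preliminary study: "the mean (5.1) and standard deviation (2.23) after treatment, as well as the mean (2.6) after false stimulation", that is, a mean and an SD for the active arm and a mean alone for the sham arm. From these the section concludes that "a minimum total sample size of 33 treatment-completers was required to achieve 90% power at" a significance level of 0.05. It then raises the number to 42, or 21 per arm, to allow for attrition, without stating an attrition rate.

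The section Outcome defines the endpoint differently: "The primary outcome is change from baseline in long-term delayed recall performance", compared between ccPAS and sham.

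The section Test grouping sets 1:1 allocation. The section Statistical analysis names the independent-sample t test for comparing two means when its assumptions hold, repeated-measures ANOVA for the before/after comparison by group, and a two-sided 5% level. No baseline mean, SD of the change or baseline-to-follow-up correlation is given anywhere.

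**The concern.** A power statement belongs to one variable and one test. Here the means and the SD describe scores after treatment, while the primary outcome is a difference between two visits. The SD of that difference depends on the SD at each visit and on the correlation between them, and the calculation uses neither the baseline SD nor the correlation. The 90% is therefore unsupported for the endpoint to which it is attached.

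The second issue is the figure of 33. It is presented as a minimum, yet it is odd in a 1:1 design and slightly too small for the t test that the protocol names. The completer target and the margin for losses both rest on it.

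**Working it through.** **Inputs.** Means 5.1 and 2.6, so a difference of 2.5; SD 2.23; 33 completers; 90% power; significance level 0.05 (Sample size calculation). Two-sided testing and the t test (Statistical analysis). Allocation 1:1 (Test grouping). The SD is quoted for the active arm only ("standard deviation (2.23) after treatment"); using it for both arms is an assumption.

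**Step 1: reproduce the protocol's figure.** The standardised difference is d = 2.5 / 2.23 = 1.121. The two-sided normal approximation for two equal arms gives

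N = 4 × (1.960 + 1.282)² / 1.121² = 33.4 in total, or 16.7 per arm.

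The normal-approximation power at 33 is 89.6%. So 33 is this result rounded down. Rounding up per arm would give 17 + 17 = 34.

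**Step 2: use the test that the protocol names.** For the two-sided t test, power comes from the noncentral t distribution with n1 + n2 − 2 degrees of freedom and noncentrality d / √(1/n1 + 1/n2). At 16 + 17 the noncentrality is 3.22 and the critical value is 2.04.

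| Completers | Split | Power |
|---|---|---|
| 33 | 16 + 17 | 87.6% |
| 34 | 17 + 17 | 88.7% |
| 35 | 17 + 18 | 89.6% |
| 36 | 18 + 18 | 90.4% |
| 42 | 21 + 21 | 94.3% |

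Ninety per cent is first reached at 36. The margin for losses is then 42 − 36 = 6, and 6/42 = 14%. Taking 33 as the target implies 42 − 33 = 9, and 9/42 = 21%.

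**Step 3: move to the change score.** For visit SDs s0 and s1 and correlation r, the SD of the change is √(s0² + s1² − 2·r·s0·s1). If both SDs are 2.23 (assumption), this reduces to 2.23 × √(2(1 − r)). Keeping the difference at 2.5 (assumption):

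| r (assumed) | SD of change | Power, 33 completers | Power, 42 completers |
|---|---|---|---|
| 0.3 | 2.64 | 75% | 85% |
| 0.4 | 2.44 | 81% | 90% |
| 0.5 | 2.23 | 88% | 94% |
| 0.7 | 1.73 | 98% | >99% |

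Under equal SDs, the calculation on after-treatment scores matches the change score only at r = 0.5. Below that it overstates power, and above it understates power.

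**Step 4: sensitivity to the equal-SD assumption.** Entry requires a long delayed recall score at least 1.0 SD below the age-matched mean (Inclusion criteria), which may make the baseline SD smaller than the after-treatment SD. With an illustrative baseline SD of 1.5, the SD of the change is 2.28, 2.13 and 1.97 at r = 0.3, 0.4 and 0.5, and power with 33 completers is 86%, 90% and 94%.

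**The case against.** The strongest reply is that 33 is not a miscalculation. It follows from a standard formula, the t-test shortfall is 90 − 87.6 = 2.4 percentage points or three completers, and the 42 enrolled more than cover it (94.3% if all complete). This stands. The protocol also states no attrition rate, so the 21% is only what 33 out of 42 implies.

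A second reply is that randomisation makes the expected baselines equal, so the expected difference in after-treatment means equals the expected difference in change. This also stands for the planned trial. Nothing in the protocol shows that the preliminary arms differed at baseline, so the 2.5 is not challenged here. The SD is a separate matter, and randomisation does not settle it.

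Three stronger readings are tempting, and the document does not support them:

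- *True power is far below 90%.* The direction is unknown. The range in step 3 runs to both sides of 90%, and its pessimistic end depends on equal SDs, which selection at baseline makes doubtful.
- *The assumed d of 1.12 is too optimistic because it exceeds the large category.* The protocol's thresholds, which "will be interpreted as small = 0.2, medium = 0.5, large = 0.8", are labels for describing effect sizes, not planning values. An assumed effect above the label contradicts nothing.
- *A null result would be taken as proof of no effect.* The protocol does not say this, and its title calls the trial a pilot.

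**Conclusion.** The point holds in limited form. The stated 90% power with 33 completers was computed for after-treatment scores and not for the primary outcome, and the document gives nothing from which power for the change score could be derived. On the quoted inputs, with a common SD of 2.23, the named two-sided t test has 87.6% power at 33 and needs 36 for 90%. This is a small shortfall from approximation and rounding, and the planned enrolment absorbs it up to a loss of 6 patients.

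The effect of the endpoint mismatch cannot be signed. With 33 completers, power runs from 75% (r = 0.3) to 98% (r = 0.7) under equal SDs and a difference of 2.5. The finding is that the claim is unsupported for the primary endpoint; it does not show that the trial is too small.

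**What to change.** Keep 42 randomised and rewrite the sample size paragraph:

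1. State the completer target as 36 (18 per arm) for 90% power on the quoted inputs, with room to lose 6 of 42 (14%); or keep 33 and state 88%.
2. Report from the preliminary study the SD of the AVLT_N5 change, or the residual SD after baseline adjustment, and recompute power for the primary analysis with it.
3. Name the test and the two-sided level used in the calculation, and say that the SD is taken as common to both arms.

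The cost is one paragraph. The restatement on the quoted inputs gives a slightly less favourable power or attrition margin; the recomputation on the change score could move power either way. No extra patients are needed to correct the statement.

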### **Diagnostic criteria**

Referring to Jak/Bondi's relevant diagnostic criteria [4]:

Symptoms of cognitive impairment (found by patients/insiders/clinicians); 2) Objective evidence of impairment in at least one cognitive function domain (memory, language, executive function, etc.); The score below the mean of the age matched population at least 1.0 standard deviation (SD); 3) Complex instrumental daily ability

---

can be slightly impaired with no impairment in remaining activities of daily living; 4) No dementia.

### **Inclusion criteria**

**Case group:** We will recruit adults aged 50–80 years who had a neuropsychological battery-confirmed initial diagnosis of aMCI. A patient meet inclusion criteria if he/she 1) having  $\geq 6$  years of education; 2) initial diagnosis of MCI and not having taken cognitive improvement medication; 3) complaining of memory loss with objective evidence (AVLT long delayed recall score at least 1.0 standard deviation lower than the mean of the age-matched population); 4) who understood and agreed to participate in this study and signed the informed consent form.

**HC group:** We will enroll adults aged 50–80 years who had a neuropsychological battery-confirmed normal cognition. A subject meet inclusion criteria if he/she 1) having  $\geq 6$  years of education; 2) No complaints of cognitive decompensation and which confirmed by objective evidence (a neuropsychological battery); 3) who understood and agreed to participate in this study and signed the informed consent form.

### **Exclusion criteria of all the subjects**

1) Comorbid tumors, serious heart, liver, kidney, hematologic disorders or infectious diseases; 2) previous other neurological disorders such as cerebrovascular disease, Parkinson's syndrome, epilepsy, dementia from various causes; 3) previous psychiatric disorders such as anxiety, depression, schizophrenia, etc. 4) severe visual and hearing impairment; 5) a history of drug and alcohol abuse/addiction; 6) presence of contraindication to MRI and contraindication to TMS treatment (e.g., pacemaker, cardiac stent, artificial heart valve, fixed plate after fracture surgery, etc.

### **Exclusion, Withdrawal, and Dropout Criteria**

#### **(1) Exclusion Criteria**

---

Misdiagnosis or inclusion of ineligible participants

Participants who deviate from the treatment protocol during the intervention

Participants who do not complete the entire course of the clinical trial, resulting in incomplete data that may affect efficacy or safety assessment.

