### **(2) Dropout Criteria**

Participants lost to follow-up during the course of the clinical trial

Participants who voluntarily withdraw from the study due to lack of efficacy, adverse reactions, or other reasons.

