### **(4) Withdrawal Criteria:**

Participants request to withdraw from the clinical research.

Inability to complete the required assessments, resulting in data collection being compromised.

Participants receive unauthorized additional treatment during the study period.

Participants develop other diseases or serious complications during the treatment period, requiring treatment or rescue measures that may affect the study protocol.

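### Two post-randomisation events, protocol deviation and non-completion with incomplete data, are listed as exclusion criteria; read with the completer-based sample size, this most naturally removes such patients from the ccPAS-versus-sham comparison

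*Protocol*

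**What the plan says.** The protocol gives entry exclusions under *Exclusion criteria of all the subjects*. A later section, *Exclusion, Withdrawal, and Dropout Criteria*, opens with a second list headed *(1) Exclusion Criteria*, which has three entries:

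- The first concerns patients who were wrongly diagnosed or should not have been enrolled.
- The second concerns conduct of the sessions: "Participants who deviate from the treatment protocol during the intervention".
- The third concerns completion and missing information: "Participants who do not complete the entire course of the clinical trial, resulting in incomplete data that may affect efficacy or safety assessment".

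Dropout, termination and withdrawal then have lists of their own. *(2) Dropout Criteria* includes "Participants who voluntarily withdraw from the study due to lack of efficacy, adverse reactions, or other reasons". *(4) Withdrawal Criteria* includes "Participants receive unauthorized additional treatment during the study period" and, as a separate entry, "Inability to complete the required assessments, resulting in data collection being compromised".

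*Sample size calculation* states that "a minimum total sample size of 33 treatment-completers was required to achieve 90% power" and raises this to 42 randomised, 21 per group, to allow for attrition. *Outcome* and *Statistical analysis* name no analysis population.

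**The concern.** Screening exclusions do no harm to a randomised comparison. Exclusions triggered by what happens after allocation can. Whether a patient departs from the treatment protocol or fails to finish may depend on the arm and on how the patient is doing. If those patients are taken out, the two groups compared are no longer the two groups that were randomised, and a difference in the change in AVLT_N5 (the primary outcome) may reflect who was left rather than what ccPAS did.

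The protocol itself gives reason to expect such loss, because it names lack of efficacy and adverse reactions among the reasons for dropout. With 21 patients per arm, a few selective removals can move the estimate noticeably.

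**Working it through.** **1. What the second exclusion list can mean.**
- It stands apart from the entry exclusions, and deviation during the intervention cannot be known at screening, so it is not a screening list.
- It also stands apart from the dropout, termination and withdrawal lists, so it is not simply a list of ways to leave the study.
- The reason attached to non-completion is the effect of incomplete data on the assessment of efficacy or safety.
- Removal from the evaluated set is the reading that fits all three facts. It is an inference; no sentence says that these patients are removed from the analysis.

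**2. Reproducing the plan's sample size.** Inputs from *Sample size calculation*: "the mean (5.1) and standard deviation (2.23) after treatment", a sham mean of 2.6, 90% power and alpha 0.05. *Statistical analysis* makes the test two-sided, and *Test grouping* gives 1:1 allocation. The SD of 2.23 is taken as common to both arms.

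- Difference = 5.1 − 2.6 = 2.5.
- n per arm = 2 × [SD × (z₀.₉₇₅ + z₀.₉₀) / difference]² = 2 × [2.23 × (1.960 + 1.282) / 2.5]² = 16.72.
- Total = 33.4 unrounded, or 34 if each arm is rounded up to 17. The stated 33 is reproduced to within rounding.
- Attrition: 33 / (1 − 0.20) = 41.25, which rounds up to 42. The plan therefore allows for 42 − 33 = 9 losses, and 9/42 = 21.4%.

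The sample size is not in error. It shows that the trial was sized for a comparison of completers and how many losses were allowed for.

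**3. What selective loss could do.** The documents do not give the pattern of loss, so everything here is an assumption: normal scores, no true effect, 21 per arm, loss from one arm only, and a two-sample t test at 5% two-sided. Results are simulated and expressed in SD units.

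| Pattern of loss in one arm | Bias (SD) | Two-sided type I error |
|---|---|---|
| 2 lowest scorers | about 0.17 | about 10% |
| 3 lowest scorers | 0.25 | 14% |
| 4 lowest scorers | 0.32 | 19% |
| 5 lowest scorers | 0.39 | 25% |
| 4 lost, correlation with outcome 0.3 | 0.10 | 6% |
| 4 lost, correlation with outcome 0.5 | 0.16 | 8% |

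The first four rows are the worst case, since the very lowest scorers leave one arm and nobody leaves the other. The last two are a milder link between loss and outcome.

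The bias raises the estimate for whichever arm loses its low scorers. If the 4 lowest leave sham instead, it is −0.32 SD, against ccPAS. If the 5 lowest leave ccPAS and the 4 lowest leave sham, most of it cancels, leaving 0.07 SD.

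**4. Loss that is balanced and unrelated to outcome.** There is no bias, only a wider interval. The standard error of the difference goes from SD × √(1/21 + 1/21) = 0.309 SD with all 42 to SD × √(1/17 + 1/16) = 0.348 SD with 33. Under the planned difference and SD, t-test power falls from 94.3% to 87.6%.

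**5. Power if all 42 are compared as randomised.** t-test power is 94.3% if the effect is undiluted. If a share of patients gains no benefit, the difference shrinks in proportion:
- 10% without benefit: 2.5 × 0.90 = 2.25, power 89.1%.
- 21.4% without benefit: 2.5 × (1 − 9/42) = 1.96, power 79.5%.

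**The case against.** The strongest reply is that removal from the analysis is read into the text. The protocol does not say what these patients are excluded from, and analysis sets and missing-data methods are commonly left to a statistical analysis plan, which is not shown. That is right as far as it goes, and the absence of a defined analysis set is not the complaint. The complaint is that a stated list labels post-randomisation events as exclusions. A statistical analysis plan with an all-randomised set would conflict with that list, which would still have to be corrected.

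Other parts of the reply stand and limit the point:

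- **Non-completion is qualified.** The list covers non-completion that leaves incomplete data, not every patient who fails to finish. A patient with no post-treatment score has no observed change under any analysis set.
- **The lists differ.** Lack of efficacy and adverse reactions are reasons for a participant's own withdrawal, and unauthorised treatment is a withdrawal criterion. Neither is on the exclusion list. They show that loss may be related to outcome, not that the plan excludes for these reasons.
- **Sizing on completers and inflating for attrition is ordinary practice.** It does not define an analysis set by itself.

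A reader might go further and infer that the rule favours ccPAS, because active stimulation could be less comfortable than sham. The documents do not support this. They say nothing about discomfort; *ccPAS Procedure* says only that the sham coils are held vertically, with the same parameters and simulated sound, and virtually no cortical effect. If ccPAS works, dropout for lack of efficacy could as well remove more poor responders from sham, which would bias against ccPAS.

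A reader might also convert the SD figures into AVLT points using 2.23. That is a post-treatment SD, while the primary outcome is change from baseline, whose SD is not given, so the results are left in SD units.

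**Conclusion.** The concern holds in a limited form. Two events that the protocol lists as exclusion criteria arise after randomisation. Together with sizing on completers, the list most naturally takes those patients out of the efficacy comparison and leaves it open to bias. That reading is an inference from the structure of the lists, not a stated analysis rule.

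Neither the direction nor the size of the bias can be derived from the documents. Under one-arm loss with no true effect, the illustration runs from about 0.10 SD with 6% type I error (4 lost, correlation 0.3) to 0.39 SD with 25% (the 5 lowest lost, worst case). Balanced loss unrelated to outcome costs precision only. This is a pilot with ten sessions over two weeks, and actual loss may be small; but the wording bears on the validity of the primary comparison and should be corrected before the data are analysed.

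**What to change.** - Delete protocol deviation and non-completion from *(1) Exclusion Criteria*. Record them as protocol deviations or treatment discontinuation.
- State that the primary ccPAS-versus-sham comparison includes all randomised patients by assigned arm.
- Continue to attempt the AVLT_N5 assessment after sessions stop, unless consent is withdrawn. This matters most, because it replaces a missing score with an observed one.
- Exclude patients found to be ineligible or misdiagnosed only on facts that predate randomisation, judged blind to arm.
- For scores still missing, use a likelihood-based model or multiple imputation. Both, in their standard form, assume data missing at random and would not generally remove loss that depends on the unseen outcome, so add a sensitivity analysis for that case.
- Keep the completer set as a sensitivity analysis.

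The cost is some rewording, a follow-up attempt for patients who stop sessions, and a possibly smaller effect estimate. The power figures above (94.3% undiluted, 79.5% if 21.4% gain no benefit) are a reason to limit loss, not to exclude patients.

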### **(3) Termination Criteria**

Termination of the trial is decided by the participants and investigators when severe adverse reactions occur during the treatment process.

Significant protocol errors or deviations occur during the trial, making it difficult to evaluate clinical efficacy.

Participants develop other diseases or serious complications during the treatment period, requiring treatment or rescue measures that may affect the study protocol.

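### As worded, the exclusion of non-completers is not limited to efficacy, so patients who stop for adverse reactions could be left out of safety reporting

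*Protocol*

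**What the plan says.** The protocol has two sets of exclusions. Those under Exclusion criteria of all the subjects apply before enrolment. Those under Exclusion, Withdrawal, and Dropout Criteria apply afterwards.

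The second set, under (1) Exclusion Criteria, includes "Participants who deviate from the treatment protocol during the intervention" and "Participants who do not complete the entire course of the clinical trial, resulting in incomplete data that may affect efficacy or safety assessment".

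Adverse reactions appear under two neighbouring headings:

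- (2) Dropout Criteria lists "Participants who voluntarily withdraw from the study due to lack of efficacy, adverse reactions, or other reasons".
- (3) Termination Criteria says "Termination of the trial is decided by the participants and investigators when severe adverse reactions occur during the treatment process".

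(4) Withdrawal Criteria then lists patients who ask to leave and those who cannot complete the assessments.

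The Outcome section is about efficacy: "The primary outcome is change from baseline in long-term delayed recall performance", with secondary measures that "included MMSE, other AVLT items, STT, SDMT, BNT, CFT" and an exploratory analysis of functional connectivity. The Statistical analysis section describes no tabulation or comparison of adverse events.

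**The concern.** An exclusion that depends on completing treatment selects patients by something that happens after randomisation. For safety, the selection is closely tied to the outcome, because a reaction to stimulation is an obvious reason for stopping early. The patients with the most to say about tolerability are then the ones most likely to meet the exclusion rule.

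The rule mentions safety assessment as something the incomplete data may affect, and its consequence is exclusion with no limit to efficacy. Someone compiling the adverse-event table from this text could reasonably leave those patients out. A tolerability statement based on completers would then lean towards no harm. Tolerability is one of the main things a pilot trial of a new paired-coil procedure can report.

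**Working it through.** **1. Who meets the rule.** Take a patient who has some of the 10 sessions, has a reaction and stops.

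- (1) Exclusion Criteria: the course is not completed and the data are incomplete, so the rule can apply. If sessions were missed or altered first, the deviation clause can apply too.
- (2) Dropout Criteria: applies if the patient leaves voluntarily because of the reaction.
- (3) Termination Criteria: applies if the reaction is severe.
- (4) Withdrawal Criteria: applies if the patient asks to leave.

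One patient can therefore meet several headings. No heading takes precedence, and none says whether events recorded before departure are kept.

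**2. How much loss the plan allows for.** The only relevant figures are in Sample size calculation: "the mean (5.1) and standard deviation (2.23) after treatment", a sham mean of 2.6, 90% power, α = 0.05 (two-sided, from Statistical analysis) and 1:1 allocation.

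- Difference: 5.1 − 2.6 = 2.5.
- Total N = 4 × [SD × (z₀.₉₇₅ + z₀.₉₀) / difference]² = 4 × [2.23 × (1.960 + 1.282) / 2.5]² = 33.4. This agrees with the stated 33 completers apart from rounding.
- Enrolment: 33 / 0.80 = 41.25, rounded up to 42. The 20% is inferred; the protocol states no rate.
- Implied allowance: 42 − 33 = 9, and 9 / 42 = 21.4%.

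These 9 are losses for any reason, not losses to harm. They show only that the plan expects a sizeable group of non-completers.

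**3. Direction of the effect.** Suppose a of n patients in an arm have a reaction, and k of those a stop and are removed. The reported rate becomes (a − k)/(n − k). This is below a/n whenever k > 0 and a < n, so the rate in that arm can only fall. The difference between arms depends on how many are removed from each.

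**4. Illustration under assumed rates.** The protocol gives no adverse-event rates. Assume reactions in 4 of 21 ccPAS and 1 of 21 sham patients, with the same share of affected patients in each arm stopping and being removed (average counts, so fractions occur).

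| Share removed | ccPAS | Sham | Difference (points) |
|---|---|---|---|
| 0% | 4/21 = 19.0% | 1/21 = 4.8% | 14.3 |
| 25% | 3/20 = 15.0% | 0.75/20.75 = 3.6% | 11.4 |
| 50% | 2/19 = 10.5% | 0.5/20.5 = 2.4% | 8.1 |
| 100% | 0/17 = 0% | 0/20 = 0% | 0 |

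The first row also covers the cases where nobody stops for a reaction, or where those who stop still have their events counted.

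**The case against.** A reader might infer that the protocol expressly prescribes a completers-only safety analysis, and that harms of ccPAS will therefore be understated. The text does not support this, for four reasons:

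- In the exclusion rule, the safety phrase describes what the incomplete data may affect. It does not define a safety population or say that recorded events are discarded.
- Voluntary withdrawal for adverse reactions is listed under dropout, and severe reactions under termination. Placing these patients under the exclusion rule is an inference from the overlap.
- No adverse-event outcome or between-arm safety comparison is specified, so there is no stated analysis for patients to fall out of.
- Understatement needs three things together: patients stop for reactions, they are handled under the exclusion rule, and their events are then left out. The protocol states neither the second nor the third.

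It can be added that a safety set is commonly defined in the SAP. None is at hand, so its absence from the protocol is not a fault.

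All of this stands, and it makes the point conditional. It does not dispose of it. The exclusion rule is stated text, it has no limit to efficacy, and it catches these patients on a literal reading. A SAP that counted events in everyone treated would sit awkwardly with that rule, so the protocol wording needs correcting in either case.

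**Conclusion.** The point holds as a conditional risk created by a stated rule. The post-enrolment exclusion of non-completers is not confined to efficacy, it overlaps with the headings that cover adverse reactions, and nothing says those patients' events are retained. If it is applied to adverse-event reporting, harms of ccPAS could be understated.

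The size is unknown. In the illustration a 14.3-point difference shrinks to anything down to 0, but the counts of 4 and 1, and the equal share removed in each arm, are assumptions. The end point of 0 requires every affected patient to stop and be removed. The bias is nil if nobody stops for a reaction or if the events are counted anyway.

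The same exclusions also weaken the randomised efficacy comparison. That is a separate matter and is not quantified here.

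**What to change.** Amend (1) Exclusion Criteria to say that neither non-completion nor deviation from treatment removes a participant from safety reporting. State that adverse events, and discontinuations because of adverse reactions, will be reported by arm for everyone who received at least one active or sham session, counting events up to and including withdrawal. Say how the four headings relate when one patient meets more than one of them.

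This changes how data are reported, not how patients are managed. It costs a change of wording and one table. Little extra information should be needed, since the reason for leaving must already be known to apply the dropout and termination headings. The reported tolerability may look less favourable than a completers-only account would.
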